## LIST OF ABBREVIATIONS AND DEFINITION OF TERMS

°C	Centigrade
°F	Fahrenheit
µg	micrograms
AE	Adverse Event/Adverse Experience
BCVA	Best Corrected Visual Acuity
eCRF	Electronic Case Report Form
CRC	Central Reading Center
CFR	Code of Federal Regulations
CTCAE	Common Terminology Criteria for Adverse Events
CBC	Complete Blood Count
DHHS	Department of Health and Human Services
DNA	Deoxyribonucleic acid
DSMB	Data Safety Monitoring Board
ETDRS	Early Treatment Diabetic Retinopathy
EDC	Electronic Data Capture
FDA	Food and Drug Administration
GCPs	Good Clinical Practices
IEC	Independent Ethics Committee
ITT	Intent-to-Treat
ICH	International Council on Harmonisation
IND	Investigational New Drug Application
IP	Investigational Product
IOL	Intraocular lens
IOP	Intraocular pressure
IRB	Institutional Review Board
IRT	Interactive Response Technology
mL	Milliliters
mm	Millimeter
SD-OCT	Optical Coherence Tomography

OGI	Open globe injury
PPV	Pars Plana Vitrectomy
PVR	Proliferative vitreoretinopathy
QID	Four Times Daily
REB	Research Ethics Board
RD	Retinal detachment
RR	Relative Risk
SAE	Serious Adverse Event/Serious Adverse Experience
US	United States
VA	Visual Acuity
WOCBP	Women of Childbearing Potential

## 1. INTRODUCTION

### 1.1. Proliferative Vitreoretinopathy

Currently, proliferative vitreoretinopathy (PVR) is the leading cause of failure of rhegmatogenous retinal detachment surgery, resulting in recurrent retinal detachment in 5%–10% of all cases. (Pastor 2008) PVR is an abnormal wound healing response that involves the proliferation of ectopic cell sheets, in which cells grow uncontrollably within the vitreous cavity as well as beneath and/or on the surface of the retina resulting in periretinal membrane formation, retinal traction, and re-detachment. Despite tremendous advances in ophthalmic surgical instrumentation and techniques, anatomic success following recurrent detachment from PVR is reported to be only 45%–80%, depending on the severity of the cases (Banerjee, Bunce, & Charteris, 2013). Furthermore, functional success (visual acuity 5/200 or better) is achieved in only 40%–80% of subjects who achieve anatomic success.

The current standard-of-care for the treatment of PVR is vitreoretinal surgery in order to remove these tractional membranes. Currently, there are no specific therapeutic agents used for the prevention or treatment of PVR. Pharmacological agents have been tested for the treatment of PVR with different activities including anti-inflammatory, anti-proliferative, anti-neoplastics, and anti-growth factor agents; albeit without reproducible success. (Asaria et al., 2001; Banerjee et al., 2017; Sundaram, Barsam, & Virgili, 2010; Wiedemann, Hilgers, Bauer, & Heimann, 1998) Although some approaches have shown success in early animal models or limited human trials, larger human studies have failed to show a beneficial effect.

A consistency in prior PVR trial design, however, has been that the agents in question were given at the time of surgery only, despite PVR being a disease that manifests 2-3 months later.

[name], observed that intraocular/vitreoretinal lymphoma suspect patients who underwent diagnostic chorioretinal biopsy did not develop epiretinal membranes or PVR when intravitreal methotrexate therapy was used to treat the lymphoma.

A Phase 1b clinical study was previously carried out at Massachusetts Eye and Ear Infirmary under a sponsor-investigator Investigational New Drug application (IND 114127). The purpose of the study was to determine the safety and tolerability of administering repeated weekly intravitreal injections of methotrexate into eyes at high-risk for the development of PVR after retinal detachment repair. Ten subjects were enrolled into a prospective, non-comparative clinical trial. Eight of these subjects had recurrent retinal detachment due to PVR after multiple prior surgeries and two subjects had retinal detachment associated with traumatic open globe injury. A protocol was designed to administer ten intravitreal injections of 400 µg/0.1 mL preservative free methotrexate over a three-month period to each of these ten subjects who underwent retinal detachment repair with silicone oil tamponade (each patient received ten injections). With a mean follow-up duration of more than three years, there were no unexpected ocular and systemic adverse events related to the drug. Furthermore, the conspicuous lack of post-operative visible PVR in eyes that were exposed to multiple injections of methotrexate suggested potential benefit of methotrexate in the prevention of recurrent retinal detachment due to PVR. (Stryjewski & Elliott, 2018)

Aldeyra is currently proposing to conduct a clinical trial to administer repeated intravitreal injections of ADX-2191, at a dose of 400 µg/0.05 mL (13 injections over a four-month period), following surgical repair of retinal detachment in eyes at high-risk for the development of PVR.

## **1.2. Therapeutic Rationale for ADX-2191 in Prevention of Proliferative Vitreoretinopathy**

No treatments to date have been found to be preventive against PVR. Once PVR develops, surgery is the only treatment.

The clinical pharmacology of ADX-2191 (intravitreal methotrexate) is based on inhibition of dihydrofolic acid reductase. Dihydrofolates must be reduced to tetrahydrofolates before they can be utilized in the synthesis of purine nucleotides and thymidylate. Therefore, methotrexate interferes with deoxyribonucleic acid (DNA) synthesis, repair, and cellular replication. Actively proliferating tissues such as malignant cells, bone marrow, fetal cells, buccal, intestinal mucosa, and cells of the urinary bladder are in general more sensitive to this effect of methotrexate. When cellular proliferation in malignant tissues is greater than in most normal tissues, methotrexate may impair malignant growth without irreversible damage to normal tissues.

Intravitreal injection provides the clinician with a means to bypass the blood retinal barrier that will provide more therapeutic doses of the methotrexate to the affected tissues than could otherwise be achieved.

## **1.3. Potential Risks and Benefits**

### **1.3.1. Potential Risks**

General risks for intravitreal injection include infection, hemorrhage; precipitated angle closures; elevated intraocular pressure (IOP) with perfusion compromise; wound leak and hypotony; anaphylactic reaction to either the agent or periprocedural materials.

In addition, known risks associated with use of intravitreal methotrexate include:

- keratopathy. Therefore, all subjects will receive lubricating eye drops and/or ointment at a minimum of four times a day, up to hourly while awake, during the injection period.
- mild conjunctival hyperemia (“red eye”) and slight pain at injection site. This hyperemia and/or slight pain is seen in almost all eyes receiving methotrexate and resolves within several hours. (Frenkel, Hendler, Siegal, Shalom, & Pe'er, 2008)

### **1.3.2. Potential Benefit**

Taking part in the clinical trial may or may not improve the subject’s surgical outcomes. However, information learned from the clinical trial will help doctors understand more about how to improve post-surgical treatments that may reduce the incidence of PVR.

## **2. CLINICAL TRIAL OBJECTIVE AND ENDPOINTS**

### **2.1. Clinical Trial Objectives**

#### **2.1.1. Primary Objective**

To evaluate the safety and efficacy of repeated intravitreal ADX-2191 injections as a pharmacologic approach to prevent recurrent retinal detachment due to PVR secondary to recurrent retinal detachment and open globe injury (OGI).

#### **2.1.2. Secondary Objective**

Part 1 will confirm the sample size to be utilized in Part 2.

### **2.2. Clinical Trial Endpoints**

#### **2.2.1. Primary Endpoints**

The primary endpoint in Part 1 and Part 2 is recurrent retinal detachment requiring reoperation within 24 weeks from time of enrollment. An evaluating investigator should determine whether the primary endpoint has been met. The primary endpoint requires verification by the Central Reading Center (CRC) before recurrent retinal detachment reoperation. In cases where CRC verification is not possible due to technical limitations with the Optical Coherence Tomography or fundus photograph, then the evaluating investigator will contact the trial medical monitor to confirm whether the primary endpoint has been met. These verification processes provide an additional level of objectivity in end point evaluation.

Definition of recurrent retinal detachment (defined as either one OR both of the following):

1. Spectral-Domain Optical Coherence Tomography (SD-OCT) demonstrating fovea-off retinal detachment (subfoveal fluid that is contiguous with a peripheral detachment);
2. Color fundus photographic documentation of a rhegmatogenous or tractional (or undetermined) retinal detachment that has progressed posterior to the Mandatory Reoperation Zone, as defined as defined by a circle centered on the fovea, with a radius halfway between the arcades and the equator (Figure 2).

Stable, peripheral rhegmatogenous or tractional (or undetermined) detachments anterior to the mid-periphery may be observed or demarcated with laser at the investigator's discretion and will not be counted as failure.

Subjects who have retinal detachment within 1-week post-operatively will be deemed to have failed Day 0 (day of surgery) and will be removed from the efficacy analysis. These will be considered "dropped" subjects. Subjects receiving investigational product during this period will continue to be followed for safety. Retinal detachment is defined as subjects who meet either of the recurrent retinal detachment imaging criteria as defined in the Primary Endpoint.

### **2.2.2. Secondary Endpoints**

The secondary endpoint in Part 1 and Part 2 is Best-corrected Visual Acuity (BCVA) change from Screening (Visit 1) level to Week 24 (as measured using an Early Treatment Diabetic Retinopathy Study [ETDRS] chart by masked technicians).

### **2.2.3. Exploratory Endpoints**

Exploratory endpoints in Part 1 and Part 2 include:

1. Total number of vitrectomy surgeries performed by Week 24
2. Total retinal attachment at Week 24
3. Total macular attachment at Week 24
4. Central macular thickness (as measured by SD-OCT) at Week 24
5. Macular epiretinal membrane (as visualized by SD-OCT) at Week 24
6. Macular and extramacular epiretinal membrane visible on color fundus photographs at Week 24
7. Percentage of eyes with intraocular pressure (IOP) < 5 mmHg at Week 24

### **2.2.4. Safety Endpoints**

Safety endpoints analyzed in Part 1 and Part 2 include:

- BCVA at distance utilizing an ETDRS chart
- IOP
- Slit-lamp evaluation
- Dilated ophthalmoscopy
- Adverse event (AE) query (reported, elicited, and observed)

## **3. INVESTIGATIONAL PLAN**

### **3.1. Overall Clinical Trial Design and Plan**

A Phase 3, multicenter, adaptive clinical trial comprised of approximately 100 evaluable eyes in Part 1 (Part 2 sample size will be determined after analysis of Part 1) at high-risk for recurrent retinal detachment due to PVR, or with OGI that may or may not have PVR.

- Subjects in the **Control cohort** (Part 1a only) will receive Standard Procedures only (defined in Section 7).
- Subjects in the **Intervention cohort** (Part 1a and 1b) will receive Standard Procedures and repeated intravitreal injections of ADX-2191 at a dose of 400 µg/0.05 mL for 16 weeks (Figure 1).

In Part 1a of the GUARD Study (prior to activation of Protocol Version 5.0, dated May 5 2021), eligible subjects will be randomized 1:1 intraoperatively to either the **Control** or **Intervention** cohort. Subjects in the **Control** cohort will receive Standard Procedures only. In Part 1b of this study (after activation of Protocol Version 5.0, dated May 5 2021), eligible subjects will no longer be randomized and all enrolled subjects will be placed in the **Intervention** Cohort. Subjects in the Intervention cohort will receive Standard Procedures and intravitreal ADX-2191 injections (Figure 1).

In Part 1a, stratification was used to balance treatment assignments within key subgroups. Subjects are to be stratified by clinical presentation (recurrent retinal detachment vs. OGI) and number of recurrent retinal detachments (>3 vs. ≤3).

Subjects enrolled in Part 1 will not be eligible to participate in Part 2 nor will they be eligible to be enrolled again during Part 1.

Clinical trial procedures to be conducted in Part 1 and Part 2 are outlined in the Schedule of Assessments (Table 1).

For Part 1, approximately 100 evaluable eyes must complete the 24-week clinical trial. Up to 50 additional subjects may be recruited to achieve the minimum number of evaluable subjects.

## **3.2. Assigning Subjects to Treatment Groups**

### **3.2.1. Subject Numbering**

Each subject screened for the clinical trial will be assigned a unique subject number that will be used to identify the subject throughout subject participation in the clinical trial. If a subject fails to be enrolled, the reason should be documented in the source documents and electronic case report form (eCRF). The subject will be considered a screen failure.

### **3.2.2. Randomization**

Per screening evaluations, all subjects will require a confirmation from the CRC and Medical Monitor that they meet the retinal imaging inclusion criteria to be eligible. If urgent (<24 hours) CRC verification is required, the Medical Monitor may unilaterally review the images and authorize the planned enrollment. In the event there is a discrepancy between the CRC and Medical Monitor review, the Medical Monitor determination will be the study-accepted reading of accountability. In Part 1a, eligible subjects are randomized to either standard procedure or standard procedure with intervention. This randomization is a 1:1 ratio within the stratified cohort groups. In Part 1b, subjects must still meet all inclusion criteria prior to enrollment. This verification process provides an additional level of objectivity in assuring subject qualification for participation in the clinical trial. If the photographic image is too poor in quality to verify eligibility, then the subject will be noted as screen failures. As noted in Section 6.8.5, in cases where preoperative color photography is technically difficult for image acquisitions (i.e., dense lens opacity, constricted pupil, intraocular bleeding, etc.), then intraoperative imaging using the operative microscope is allowed.

In Part 1a, those subjects that meet enrollment criteria will enter the randomization process and will be allocated to the Control vs. Intervention cohorts. The assignment to cohort will be

revealed intraoperatively at the conclusion of the surgery to the investigator after retinopexy has been applied. Note: administratively, the randomization may occur prior to surgery if logistically required by the site. However, the investigator must remain blinded to randomization until the defined timepoint. When administrative randomization occurs prior to surgery, all measures must be taken to avoid indicating assigned treatment group prior to conclusion of surgery.

Randomization scheme will be managed by an Interactive Response Technology (IRT) system. Subjects will be randomized by indication (recurrent retinal detachment due to PVR or any RD associated with OGI).

Eligible subjects will be randomized 1:1 intraoperatively to either group:

**Control:** Standard Procedures

**Intervention:** Standard Procedures with the addition of repeated intravitreal injections of ADX-2191 until post-operative Week 16.

In Part 1b of the GUARD study with activation of Protocol Version 5.0 (dated May 5 2021), eligible subjects will no longer be randomized and all enrolled subjects will be placed in the Intervention Cohort.

### **3.3. Safety Oversight**

During the clinical trial, subject safety will be monitored on a continuous basis by the Sponsor Medical Monitor until the last subject completes the last scheduled clinical trial assessment.

### **3.4. Data Safety Monitoring Board**

Masked safety data will be reviewed throughout the clinical trial by Aldeyra.

An external Data Safety and Monitoring Board (DSMB) will review selected unmasked data for safety assessment. The review frequency, criteria, and the process for making recommendations will be defined in the charter.

### **3.5. Clinical Trial Duration for Individual Subjects**

The clinical trial consists of 16 clinic visits over a period of approximately 24 weeks.

### **3.6. Clinical Trial Population Selection**

The intended population will be adult subjects undergoing pars plana vitrectomy for the following indications:

1. Recurrent retinal detachment due to PVR with documented starfolds in at least three cumulative clock hours on retinal imaging. (Imaging modality methods defined in Section 6.8.5).
2. Retinal detachment associated with open globe injury (the open globe retinal detachments may or may not have PVR at the time of enrollment).

### **3.6.1. Inclusion Criteria**

Subjects meeting ALL of the following criteria will be considered eligible for clinical trial entry:

1. Subject is 18 years or older of any gender or any race
2. Subjects are undergoing pars plana vitrectomy for the following indications:
  - a. Recurrent retinal detachment due to proliferative vitreoretinopathy (PVR) with documented starfolds in at least three cumulative clock hours on retinal imaging
  - b. Retinal detachment associated with open globe injury (OGI)
3. Subjects must undergo silicone oil tamponade as part of the pars plana vitrectomy
4. Investigators must agree to follow surgical principles as outlined in Section 6.9
5. At the conclusion of the retinal detachment surgical repair, the retina must be completely reattached, and in the surgeon's best judgment, the subject should have a high likelihood of benefitting from enrollment in the clinical trial
6. Subject is willing and able to provide written informed consent, comply with clinical trial procedures, and return for all clinical trial visits
7. Subjects of childbearing potential, both male and female, must agree to use two forms of birth control for the duration of the clinical trial. Males should continue to use the two forms of birth control for a minimum of three months after last injection (30 days after completion of Visit 16/Week 24). Females of childbearing potential must use the two forms of birth control for a minimum of 30 days following their last injection.
8. For females of child-bearing potential, subjects must have a negative pregnancy test at Screening and not lactating

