Pre-Injection Assessment By Treating Investigator 				X	X	X	X	X	X	X	X	X	X	X	X	X	X
Dispense Artificial Tears/Lubricating Ointment		X	X	X	X	X	X	X	X	X	X	X	X	X	X	X	X
Adverse Events		X	X	X	X	X	X	X	X	X	X	X	X	X	X	X	X

1. Physical exam includes height and weight.

2. Clinical laboratory testing includes chemistry and hematology. Refer to Section 6.7 for more detail.

3. Pregnancy test for all women of childbearing potential. Post randomization (Part 1a) and all WOCBO Part 1b, pregnancy testing only required for intervention treatment group. During the clinical trial, best corrected visual acuity and ocular exams will be performed in both eyes at Visit 1/Screening and Visit 16/Week 24/EOs/ET visits.

4. Best Corrected Visual Acuity and ocular exam will be performed in both eyes at Visit 1/Screening and Visit 16/Week 24/EOs/ET visits. During the clinical trial, best corrected visual acuity and ocular exams will be performed in study eye only.

5. Fundus photographs measured by ultra-wide field imaging. However, standard 4-field or 7-field photos if ultra-wide field imaging is not available. At Screening, fundus photographs not required for subjects with open globe injury and retinal detachment.

6. Post randomization, pregnancy testing required for intervention treatment group.

7. The initial ADX-2191 intravitreal injection may be performed while in the operating room Day 0 or on post-operative Day One.

8. Pre-Injection Assessment by treating investigator to include visual acuity assessment, slit-lamp examination, intraocular pressure measurement, and dilated ophthalmoscopy. Refer to Section 6.13 for more detail. The screening visit should optimally occur within 2 weeks of the Day of Surgery (Visit 2).

9. The screening visit should optimally occur within 2 weeks of the Day of Surgery (Visit 2).

10. If a separate evaluating investigator is not available, the assessment may be made by the treating investigator and noted in the eCRF (section 6.8.4).

11. As of Protocol Version 5.0 (dated May 5 2021), eligible subjects will no longer be randomized and all enrolled subjects will be placed in the Intervention Cohort.

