### **3.7. Strategies for Recruitment and Retention**

Subjects will be recruited directly from the investigative sites' patient population or will be referred for treatment by other physicians. Once enrolled, subjects will be provided with the visit schedule and reminders from the clinical trial staff in advance of their visits to assist with compliance to the schedule of events for the clinical trial.

Subjects who discontinue early from investigational product treatment will complete the end-of-study visit (Week 24) at time of discontinuation. The Sponsor and Investigator will make all efforts to retain all subjects in the clinical trial until the end-of-study visit (Week 24) and to follow-up with early discontinued subjects for safety purposes.

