#### **4.4. Handling of Subject Withdrawals or Subject Discontinuation of Clinical Trial Intervention**

Subjects that are dropped from the clinical trial prior to administration of the interventional investigational product or whom fail to achieve intraoperative complete retinal reattachment will be considered screen failures and will not be enrolled or included in analysis.

Subjects who have retinal detachment within 1-week post-operatively will be deemed to have failed Day 0 (day of surgery) and will be removed from the efficacy analysis. These will be considered “dropped” subjects.

Any subject receiving the investigational product will be followed for safety throughout the scheduled course of the clinical trial, or until the subject has reached a status of un-reachable.

It is anticipated that there will be a potential drop-out rate of up to 20%. To assure the clinical trial meets the required approximate 100 evaluable eyes for analysis, additional subjects may need to be enrolled to meet this goal.

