## **6.7. Safety Testing**

Samples of blood and urine will be collected for clinical laboratory tests which includes general safety parameters (hematology, serum chemistry, and urinalysis) and pregnancy. All subjects will provide blood samples for clinical laboratory testing for chemistry and hematology, as well as urine for a urinalysis at Screening Visit (Visit 1) and Final Visit (Visit 16 / Week 24; or at subjects last visit when subject is terminated and follow up is not available through Week 24, if possible).

Chemistry profile includes blood urea nitrogen (BUN), calcium, chloride, creatinine, creatinine to BUN ratio, carbon dioxide (CO2), potassium, sodium, albumin, alanine aminotransferase (ALT), alkaline phosphatase (ALP), Aspartate aminotransferase (AST), total bilirubin, and total protein.

Hematology profile includes hematocrit, hemoglobin, platelets, red blood cells, and white blood cells (without differentials).

For women of childbearing potential (WOCBP) enrolled in the Intervention cohort, a pregnancy test will be collected at the Screening Visit (Visit 1), and prior to each injection of ADX-2191, through Visit 16 / Week 24. Results must be available and confirmed to be negative before the subject may be enrolled in the clinical trial. IP must be discontinued for any subject with a positive pregnancy test result.

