## **6.8. Ophthalmic Examinations**

### **6.8.1. Best-Corrected Visual Acuity**

BCVA will be collected at Screening (V1), Day 1 (V3), Weeks 1 (V4), 4 (V7), 8 (V11), 12 (V13), 16 (V15), and 24 (V16). The BCVA will be measured using ETDRS chart by masked technicians at a standard photopic light level of at least 85 cd/m^2. These assessments are to be conducted in both eyes at Visit 1(screening) and Visit 16 (end of study/early termination). The study eye only may be examined at other time points.

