#### **8.7. Reporting Pregnancies**

Pregnancies for women will be reported from the time the subject signs the informed consent form through final clinical trial visit or 30 days after the last IP administration, whichever is later. Males will report pregnancy of their partners through 90 days after the last IP administration.

To ensure subject safety, each pregnancy in a subject on IP must be reported to Pharmacovigilance within 24 hours of learning of its occurrence. Subjects who become pregnant will be withdrawn from the clinical trial. The pregnancy should be followed up to determine outcome, including spontaneous or voluntary termination, details of the birth, and the presence or absence of any birth defects, congenital abnormalities, or maternal and/or newborn complications.

Pregnancy should be recorded on a subject's source documents and a Pregnancy Notification and Outcome Form and reported by the investigator to Pharmacovigilance using the same procedure for reporting SAEs detailed in Section 8.6.2. A pregnancy, by itself, is not an SAE. Pregnancy follow-up should also be recorded and should include an assessment of the possible relationship to the IP of any pregnancy outcome. Any pregnancy-related SAE (e.g., spontaneous abortion, birth defect) or any other SAE experienced during pregnancy must be recorded on a separate SAE Report Form and reported per SAE reporting procedures in Section 8.6.2.

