#### **9.4.5. Primary Efficacy Analyses**

The primary efficacy variable of recurrent of retinal detachments (defined in Section 3.6) due to PVR requiring re-operation within six months from enrollment will be measured as binary variable (indicating recurrent of detachment or not). Briefly, a 95% confidence interval around the proportion of retinal detachment in drug-treated subjects will be generated, and the primary endpoint will have been deemed to have been met if the upper bound of the confidence interval is lower than the weighted average historical control detachment rate. The primary efficacy analyses will be conducted on the ITT population with observed data only. Subjects who discontinue investigational treatment early will be encouraged to stay for any remaining safety assessments until the conclusion of the clinical trial. Subjects who have retinal detachment within 1-week post-operatively will be deemed to have failed Day 0 (day of surgery), and will be removed from the efficacy analysis.

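### Male contraception in criterion 7: the three-month minimum after the last injection and its gloss, 30 days after Visit 16, are counted from different dates and are not equivalent

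*Combined protocol and SAP*

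**What the plan says.** Criterion 7 appears in the same words in the synopsis and in Section 3.6.1. Men and women of childbearing potential use two forms of birth control throughout the trial. Men then continue for "a minimum of three months after last injection (30 days after completion of Visit 16/Week 24").

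Other places bear on how this is read:

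- Section 6.11 puts the last scheduled injection at Week 16 (Visit 15).
- Section 7 puts Visit 16 at Week 24. It asks for no less than 24 weeks from surgery, yet also gives a tolerance of two weeks either side. It counts event weeks by calendar week.
- Section 8.7 sets a different duty for men, counted from the last dose: "Males will report pregnancy of their partners through 90 days after the last IP administration".
- Section 3.7 says that subjects who stop treatment early "will complete the end-of-study visit (Week 24) at time of discontinuation". Table 1, footnote 4 ("Visit 16/Week 24/EOs/ET visits") and Section 6.8.1 ("Visit 16 (end of study/early termination") also use Visit 16 as the early-termination visit.
- Section 4.4 points the other way: "Any subject receiving the investigational product will be followed for safety throughout the scheduled course of the clinical trial". So does Section 9.4.5: "Subjects who discontinue investigational treatment early will be encouraged to stay for any remaining safety assessments until the conclusion of the clinical trial".

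**The concern.** The parenthesis reads as a restatement of the three-month rule, so a coordinator could take it as the practical stopping date and give it to the subject. It is tied to a visit whose distance from the last injection is not fixed. When that distance is short, the gloss ends before three months have passed; when it is long, the gloss runs well past them.

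What is at stake is the clarity of a safety instruction. Section 1.2 describes the drug as interfering with DNA synthesis, and the sponsor chose a three-month minimum for men. An eligibility criterion that men must agree to should give one stopping date.

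**Working it through.** **Inputs.** Last scheduled injection: Week 16, nominal day 16 × 7 = 112 (Section 6.11). Visit 16: Week 24, nominal day 24 × 7 = 168 (Section 7). Gloss: Visit 16 + 30 days (criterion 7). Day count used for men elsewhere: 90 days after the last dose (Section 8.7). Three calendar months span 89 to 92 days.

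**The plan's own equivalence, nominal schedule.** 168 + 30 − 112 = 86 days.

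- Against 90 days: 90 − 86 = 4 days short. Against the shortest three calendar months: 89 − 86 = 3 days short.
- Against 12 weeks: 86 − 84 = 2 days to spare. The protocol does use four-week months. The primary endpoint runs over 24 weeks in Section 2.2.1 and over six months in Section 9.4.5 (24 / 6 = 4 weeks per month). The injections run over 16 weeks in the synopsis and over four months in Section 1.1 (16 / 4 = 4). Three such months are 3 × 4 × 7 = 84 days.

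**General rule.** If Visit 16 is held L days after the last injection, the gloss gives L + 30 days.

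- L + 30 = 90 gives L = 60, so coverage is under 90 days whenever L is below 60.
- L + 30 = 84 gives L = 54, so coverage is under 84 days whenever L is below 54.
- The schedule has L = 168 − 112 = 56, which lies between the two thresholds. That is why the verdict for a completer depends on the length of a month.

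**Visit window, injection on day 112.**

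- Visit 16 at Week 22 (day 154): 154 + 30 − 112 = 72 days.
- Visit 16 at Week 26 (day 182): 182 + 30 − 112 = 100 days.
- If the requirement of at least 24 weeks overrides the minus side of the tolerance, the 72-day case drops out.

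**Calendar weeks.** With surgery and visits on weekdays, the Monday of Week One falls on day 3 to day 7, so the Week 16 injection falls between day 3 + 105 = 108 and day 7 + 4 + 105 = 116. With Visit 16 on day 168, the gloss gives 198 − 116 = 82 to 198 − 108 = 90 days.

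**Visit 16 held as an early-termination visit.** The documents give no interval between last injection and early termination, so L is an assumption here.

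| Assumed L (days) | Gloss, L + 30 | Short of 90 | Short of 84 |
|---|---|---|---|
| 0 | 30 | 60 | 54 |
| 14 | 44 | 46 | 40 |
| 28 | 58 | 32 | 26 |
| 54 | 84 | 6 | 0 |
| 60 | 90 | 0 | none |

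**The opposite direction.** Under Section 6.9, injections stop after a re-detachment that needs reoperation, and the subject is followed to Week 24. With a last injection at Week 4, 8 or 14, the gloss gives 198 − 28 = 170, 198 − 56 = 142 or 198 − 98 = 100 days, all longer than three months.

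**The case against.** The strongest reply is that the rule itself is explicit and correctly anchored. A parenthesis cannot shorten a stated minimum, and a site satisfies both phrases by using the later date. This stands. A reader might infer that the protocol lets men stop 30 days after any final visit; the documents do not support that, because the words just before the parenthesis forbid it.

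Second, a reader might infer that every man who completes the schedule is under-covered. That depends on the length of a month. The 90 days in Section 8.7 belong to pregnancy reporting, not to contraception, and the protocol's loose usage of 24 weeks for six months and 16 weeks for four makes 84 days a defensible reading, which 86 days meets. This also stands: the nominal shortfall is conditional and at most a few days.

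Third, an early Visit 16 is possible but not the default. Section 4.4 follows treated subjects through the scheduled course unless they become unreachable, Section 9.4.5 encourages early stoppers to stay, and Section 3.7 itself goes on to commit to retention until Week 24. Section 6.7 treats a final visit before Week 24 as the exception: "or at subjects last visit when subject is terminated and follow up is not available through Week 24". A site could also read Week 24 in the gloss as the calendar time point, which lengthens cover for an early stopper. All of this limits how often the gap can arise. It does not remove it, because Section 3.7 places the end-of-study visit at discontinuation and two other places label Visit 16 as the early-termination visit.

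**Conclusion.** The point holds as an ambiguous gloss in an operative safety instruction; severity is minor. The mismatch of anchors and the formula L + 30 are certain. The nominal 86 days is short by 4 against 90 and sufficient against 84. The material gap needs two things together: Visit 16 held early, and a site that counts 30 days from the visit actually held. Coverage is then below 90 days for L under 60 and below 84 for L under 54. The 30 to 44 days rest on an assumed lag of 0 to 14 days.

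The number of men affected cannot be derived from the documents. A reader might infer harm to partners or offspring; the documents give no data on male-mediated risk at this intravitreal dose, so none is shown. Sample size, power and analysis are unaffected.

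**What to change.** Delete the parenthesis in criterion 7 in the synopsis and in Section 3.6.1. State instead that males use two forms of birth control for the duration of the trial and until at least 90 days after the last injection, whichever is later, regardless of the date of Visit 16 or early termination. This uses the anchor and day count of Section 8.7 and settles what three months means. For a nominal completer it ends 90 − 56 = 34 days after Week 24, four days later than the gloss.

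The cost is wording in two places, plus the consent form if it repeats the phrase (its pages are not in the document reviewed). No visit, data item or analysis changes.
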